9. SAFETY EVALUATION

All summaries and analysis of safety data will be presented for the Safety Analysis Population. Safety summaries will be presented overall and by treatment group.

Listings will be sorted by treatment group, subject ID, parameter (if applicable), and visit.

Continuous variables will be summarized using the following descriptive statistics: n (non-missing sample size), mean, standard deviation, median, maximum and minimum. All categorical measures will be summarized by the frequency and percentages (based on the non-missing sample size) of observed levels.

9.1. Demographic and Other Baseline Characteristics

Summaries of age, sex, ethnicity, race, duration of symptoms, transplant type, and categorical age range will be presented by treatment group, overall and by site ([Table 11](#), [Table 12](#), [Table 13](#), and [Table 14](#)). Ethnicity is categorized as Hispanic or Latino, or not Hispanic and not Latino. In accordance with NIH reporting policy, subjects may self-designate as belonging to more than one race or may refuse to identify a race, the latter reflected in the CRF as “No” to each racial option.

Individual subject listings ([Appendix 3](#)) will be presented for all demographics ([Listing 6](#)); pre-existing medical conditions ([Listing 7](#)); vital signs and oral temperature ([Listing 27](#)); and concomitant medications ([Listing 32](#)).

9.1.1. Prior and Concurrent Medical Conditions

All current illnesses and past pre-existing medical conditions will be MedDRA® coded using MedDRA dictionary version 24.0 or higher.

Summaries of subjects’ pre-existing medical conditions will be presented by treatment group ([Table 15](#)).

Individual subject listings will be presented for all medical conditions ([Listing 7](#)).

9.1.2. Prior and Concomitant Medications

Summaries of medications that were started prior to dosing and continuing at the time of dosing, as well as any medications collected through visit 12 (Day 180) or early termination, whichever occurs first, will be presented by WHO Drug Levels 1 and 2 and treatment group ([Table 115](#)).

Individual subject listings will be presented for all concomitant medications ([Listing 32](#)).

9.2. Measurements of Treatment Compliance

The number of subjects who received any treatment and the number of subjects who received all scheduled treatments through Days 7, 14, 21, and 28 is presented by treatment group in [Table 6](#). The number of subjects that received any additional nitazoxanide and additional nitazoxanide after Day 28 will also be included in the table. A subject is considered compliant with the assigned study product if they take at least 75% of the scheduled doses through 28 days and do not receive additional nitazoxanide before the primary outcome is observed. [Table 10](#) provides the number of subjects compliant with study product, the mean cumulative number of pills taken and the mean percentage of pills taken for each treatment group at Days 7, 14, 21, and 28. A listing of treatment compliance by subject is presented in [Listing 8](#).

9.3. Adverse Events

When calculating the incidence of adverse events (i.e., on a per subject basis), each subject will only be counted once and any repetitions of adverse events within a subject will be ignored; the denominator will be the total number of subjects in the Safety Population. All adverse events reported will be included in the summaries and analyses.

An overall summary of adverse events is presented in [Table 49](#). [Table 50](#) presents subject-level rates and differences between treatment groups for the following safety outcome measures:

- Incidence of unsolicited non-serious adverse events through 60 days (Day 60)
- Incidence of laboratory adverse events (WBC, Hemoglobin, Platelet count, Creatinine, Alkaline Phosphatase, ALT, AST, BUN, and Bilirubin) through 60 days (Day 60)
- Incidence of protocol-specified serious adverse events through 60 days (Day 60)
- Incidence of hospitalization through 60 days (Day 60)

[Table 51](#) repeats these subject-level rates and differences between treatment groups for the subjects that do not report chromaturia.

9.3.1. Unsolicited Adverse Events

The proportion of subjects reporting at least one unsolicited adverse event will be summarized by MedDRA System Organ Class (SOC) and Preferred Term. Denominators for percentages are the number of subjects in the safety population.

Adverse events by subject will be presented in [Listing 21](#).

The following summaries for unsolicited adverse events will be presented by MedDRA System Organ Class, Preferred Term, and treatment group:

- Summary of adverse events occurring in 5% of subjects ([Table 52](#));
- Subject incidence and total frequency of adverse events over time by study phase with 95% CI (Treatment Phase, Longitudinal Phase) ([Table 53](#), [Table 54](#), and [Table 55](#))
- Summary of severity and relationship to study product ([Table 56](#), [Table 57](#), and [Table 58](#));
- Summary of incidence and total frequency of related adverse events during the treatment phase (Days 1 – 28) ([Table 59](#))
- Subject listing of serious adverse events ([Table 60](#));
- Subject listing of non-serious adverse events of moderate or greater severity ([Table 61](#));
- Bar chart of related adverse events by MedDRA SOC and severity ([Figure 25](#));
- Bar chart of incidence of related adverse events by MedDRA SOC and maximum severity ([Figure 26](#));

9.4. Deaths, Serious Adverse Events and other Significant Adverse Events

A subject listing of deaths and serious adverse events ([Table 60](#)) will be presented including Subject ID, Adverse Event Description, Adverse Event Onset Day and Duration, Reason Reported as an SAE, Severity, Relationship to Treatment, Alternate Etiology if not Related, and Outcome. A subject level listing of deaths including cause of death will be included in [Listing 30](#).

9.5. Pregnancies

For any subjects in the Safety population who became pregnant during the study, every attempt was made to follow these subjects to completion of pregnancy to document the outcome, including information regarding any complications with pregnancy and/or delivery. A listing of pregnancies and outcomes will be presented ([Listing 33](#), [Listing 34](#), [Listing 35](#), [Listing 36](#), and [Listing 37](#)).

9.6. Clinical Laboratory Evaluations

Safety laboratory parameters are defined in Section [4.5.3](#). Chemistry parameters include creatinine, alkaline phosphatase, AST, ALT, BUN, and total bilirubin. Hematology parameters include WBC, hemoglobin, and platelets. In addition, T-Cell subsets were also collected and include CD3 (CD3+), CD3/lymphocytes (CD3 + %), CD3 (CD3+), CD4/lymphocytes (CD4 + %), CD8 (CD8+), and CD8/lymphocytes (CD8 + %) and other hematology parameters (neutrophil, lymphocyte, eosinophil, monocyte, hematocrit, and mean corpuscular volume) were collected. The distribution of laboratory results by time point, treatment group, and maximum severity will be presented in [Table 64](#), [Table 65](#), [Table 66](#), [Table 67](#), [Table 68](#), [Table 69](#), and [Table 70](#) for chemistry parameters and in [Table 84](#), [Table 85](#), [Table 86](#), and [Table 87](#) for hematologic parameters. The distribution of abnormal laboratory results related to study treatment by time point, treatment group, and maximum severity will be presented in [Table 71](#), [Table 72](#), [Table 73](#), [Table 74](#), [Table 75](#), [Table 76](#), and [Table 77](#) for chemistry parameters and in [Table 88](#), [Table 89](#), [Table 90](#), and [Table 91](#) for hematologic parameters. Descriptive statistics including mean, standard deviation, median, minimum, and maximum values by time point, for each laboratory parameter, will be summarized in [Table 78](#), [Table 79](#), [Table 80](#), [Table 81](#), [Table 82](#), and [Table 83](#) for chemistry parameters and [Table 92](#), [Table 93](#), and [Table 94](#) for hematologic parameters. Additionally, descriptive statistics will be summarized in [Table 95](#), [Table 96](#), [Table 97](#), [Table 98](#), [Table 99](#), [Table 100](#), [Table 101](#), [Table 102](#), [Table 103](#), [Table 104](#), [Table 105](#), and [Table 106](#) for the T-Cell subset parameters and other hematologic data that were not evaluated for abnormality.

Listing of abnormal laboratory results for chemistry and hematologic parameters will be presented in [Table 62](#) and [Table 63](#), respectively. [Listing 24](#) and [Listing 25](#) will provide a complete listing of individual clinical laboratory results with applicable reference ranges. A complete listing of individual T-Cell subset results will be provided in [Listing 26](#).

9.7. Vital Signs and Physical Evaluations

Vital sign measurements included weight, systolic blood pressure, diastolic blood pressure, respiration, pulse, and oral temperature. Vital signs were assessed at Day 1, Day 7, Day 14, Day 21, Day 28, Day 60, Day 120, and Day 180. Height was also measured at Day 1. Vital signs will be tabulated by visit and treatment group ([Table 109](#), [Table 110](#), [Table 111](#), [Table 112](#), [Table 113](#), and [Table 114](#)). All vital signs will be listed by subject and time point in [Listing 27](#).

Physical Examinations were performed at Day 1 and Day 28. The change in physical examination data from Day 1 will be summarized for each visit by treatment group for subjects in the Safety population ([Listing 31](#)).

9.8. Concomitant Medications

Concomitant medications will be coded to the Anatomical Therapeutic Classification (ATC) using the WHO Drug Dictionary. The use of prior and concomitant medications taken during the study will be recorded on the CRFs. A by-subject listing of concomitant medication use will be presented ([Listing 32](#)). The use of concomitant medications during the study will be summarized by ATC1, ATC2 code and treatment group for the Safety Population ([Table 115](#)).

9.9. Other Safety Measures

Hospitalizations were collected as an outcome measure for the secondary objective and therefore were not reported as serious adverse events. [Table 50](#) presents subject-level rates and differences between treatment groups for the incidence of hospitalization through 60 days. The protocol calls for the average number of days of hospitalization to be estimated and compared between treatment groups using a two-sample t-test. However, due to early closure of the study, the number of subjects is too small to meet the normality assumptions of the t-test; therefore Wilcoxon-Mann-Whitney exact rank sum tests will be used to compare the number of days of hospitalization between treatment and placebo through Day 28 and Day 180 in the Safety Population ([Table 107](#)). A listing of all hospitalizations is presented in [Listing 28](#).

10. IMMUNOGENICITY

Summary statistics including the number of subjects with a valid result, geometric mean titer and 95% CI, median, minimum, and maximum will be provided by study day and treatment group for Norovirus-specific serum and stool IgA, IgM, and IgG in [Table 37](#). In addition, geometric mean fold-rise and proportion of responders (defined as four-fold or greater increase from baseline) with 95% confidence intervals will be displayed in [Table 38](#). Confidence intervals for the proportion of responders will be Wilson score two-sided 95% CIs. [Table 37](#) and [Table 38](#) will also provide summaries for Total Serum IgG and the ratio of Norovirus-specific IgG to Total IgG for each study day and treatment group.

The change in Norovirus-specific serum and stool IgA, IgM, and IgG between Day 1 and Day 28 and Day 1 and Day 60 will be assessed using analysis of covariance (ANCOVA) adjusting for baseline assay value. The analysis will be conducted in the mITT population. [Table 39](#) will present the observed means and standard deviations of the change in Norovirus-specific serum and stool IgA, IgM, and IgG between Day 1 and Day 28 and Day 1 and Day 60 for each treatment group. Levene's test and normality checks will be carried out to check if the assumptions of ANCOVA are met. If assumptions of ANCOVA have been met, the adjusted mean, standard error, and 95% confidence intervals will also be presented for each treatment group. The p-value for the test of between treatment differences will also be presented. If the assumptions of ANCOVA are not met, transformations of the change in assay variable may be utilized to correct any skewness in residuals or heterogeneity of the variances. If a transformation of the dependent variable is used, a footnote in the table will denote which transformation was used in the analyses. If the assumptions of ANCOVA cannot be met through transformation of the dependent variable, only the observed mean, standard deviation and 95% confidence intervals of the unadjusted change in Norovirus-specific serum and stool IgA, IgM, and IgG between Day 1 and Day 28 and between Day 1 and Day 60 will be reported.

A mixed effects model will be used to compare the change in each Norovirus-specific serum and stool IgA, IgM, and IgG between nitazoxanide and placebo for each assay. Norovirus-specific serum and stool IgA, IgM, and IgG measured on study days 1, 28 and 60 will be included in the mixed effects model. Below the mixed effects model for Norovirus-specific serum IgA is described. Analyses for each assay type will be performed in a similar manner.

The mean Norovirus-specific serum IgA with 95% confidence intervals will be displayed graphically for each time point for each treatment group. If a linear relationship between Norovirus-specific serum IgA and time is observed for both groups, then a model that makes use of this simplifying assumption will be used. Letting Y denote Norovirus-specific serum IgA, t denote the time point (study day), and i be a subject index, and letting $treatment=1$ for those in the nitazoxanide group and $treatment=0$ for those in the placebo group, we will model serum IgA as:

$$Y_{it} = \beta_0 + \beta_1 t + \mu_i + \alpha_i t + \beta_2 treatment + \beta_3 treatment \cdot t + \epsilon_{it},$$

If the relationship is nonlinear, then a transformation (e.g. log transformation) may be applied, or we will fit the following model, which relaxes the linearity assumption. Let $1_{[t=k]}$ denote an indicator variable taking the value one when $t=k$ and zero otherwise. Let u_i denote the random intercept for subject i and let α_i denote the random slope for subject i , and assume these random effects are normally distributed with mean zero. Then without assuming linearity, the serum IgA for subject i at time t can be modeled as:

$$Y_{it} = \beta_0 + \mu_i + \alpha_i t + \beta_1 \cdot treatment + \beta_2 1_{[t=28]} + \beta_3 1_{[t=28]} \cdot treatment + \beta_4 1_{[t=60]} + \beta_5 1_{[t=60]} \cdot treatment + \epsilon_{it},$$

The error terms, ϵ_{it} , are assumed to be independent and normally distributed with constant variance and mean zero. If residual plots indicate that variance is not constant and/or the errors are not normally distributed, transformations (e.g., the log transformation of the response) will be considered. Choice of covariance structures for the random effects (e.g., compound symmetric and autoregressive), will be explored.

In this model, the expected serum IgA for the placebo group on Day 1 is β_0 , and on Day 28 ($t=28$) is $\beta_0 + \beta_2$. Therefore, the expected change from time Day 1 to Day 28 is β_2 for the placebo group. The expected serum IgA for the nitazoxanide group on Day 1 is $\beta_0 + \beta_1$, and on Day 28, it is $\beta_0 + \beta_1 + \beta_2 + \beta_3$. Therefore, the expected change for the nitazoxanide group from Day 1 to Day 28 is $\beta_2 + \beta_3$. Thus, the difference in rate of change in Norovirus-specific serum IgA from Day 1 to Day 28 between nitazoxanide and placebo groups is, on average, β_3 . The interpretation for parameter β_5 is similar.

The analyses will be performed on the Immunogenicity population. [Table 40](#) will present the coefficient estimates for the mixed effects model for the Norovirus-specific serum IgA assay. [Table 41](#), [Table 42](#), [Table 43](#), [Table 44](#), and [Table 45](#) will present the coefficient estimates for the mixed effects models for the remaining assay types.

The relationship between change in total lymphocyte count between Day 1 and 180 and the day of initial clinical resolution of symptoms will be evaluated using Pearson correlations. A Fisher's Z-transformation will be applied to the Pearson correlations in both the nitazoxanide and placebo groups. These will then be compared using a Z-test and the p-value will be reported along with the Pearson correlations and 95% confidence intervals in [Table 46](#). The following relationships will also be evaluated in [Table 46](#):

- Change in T cell subsets between Day 1 and 180 and the day of initial clinical resolution of symptoms.
- Change in total lymphocyte count between Day 1 and 180 and the first day of undetectable quantitative Norovirus PCR (see viral load in Section 3.3).
- Change in T cell subsets between Day 1 and 180 and the first day of undetectable quantitative Norovirus PCR (see viral load in Section 3.3).

Similarly, [Table 47](#) will evaluate the following relationships:

- Change in Norovirus-specific serum and stool IgA, IgM, and IgG from Day 1 to Day 28 and the day of initial clinical resolution of symptoms.
- Change in Norovirus-specific serum and stool IgA, IgM, and IgG from Day 1 to Day 60 and the day of initial clinical resolution of symptoms.
- Change in Norovirus-specific serum and stool IgA, IgM, and IgG from Day 1 to Day 28 and the first day of undetectable quantitative Norovirus PCR (see viral load in Section 3.3).
- Change in Norovirus-specific serum and stool IgA, IgM, and IgG from Day 1 to Day 60 and the first day of undetectable quantitative Norovirus PCR (see viral load in Section 3.3).

All immunogenicity variables will be listed by treatment group, subject, and visit in [Listing 20](#) and [Listing 21](#). Total lymphocyte counts, and T-Cell subsets will be listed in [Listing 23](#) and [Listing 24](#), respectively.

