11 STATISTICAL CONSIDERATIONS

11.1 Study Hypotheses

A formal hypothesis test is planned to compare nitazoxanide to placebo with respect to the primary efficacy outcome measure. The time from randomization until clinical resolution of Norovirus for at least 48 hours through 180 days will be compared between the two study arms.

The null hypothesis is that there is no difference in time until clinical resolution between study arms, with a two-sided alternative. The test for primary efficacy hypothesis will be conducted using a Log-Rank test at the 5% two-sided level of significance.

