Serum Immunoglobulin Testing (Serum total Ig and Norovirus-specific levels): Day 1 will assess baseline values, Day 28 will assess end of treatment levels. The proportion of subjects with ≥ 4 -fold rise in Norovirus-specific Ig titers from Day 1 will be assessed at Day 28 comparing

the nitazoxanide treatment group to the placebo group. In addition, the ratios of Norovirus-specific IgG to total IgG will also be compared between the nitazoxanide and placebo groups.

For exploratory outcome 22, an ANCOVA model will first be used to compare the treatment and placebo groups with respect to difference in changes of Norovirus-specific serum and stool IgA, IgM and IgG between Day 1 and Day 28 and between Day 1 and Day 60 (for stool only). A mixed effects model will then be used to compare the treatment and placebo groups with respect to difference in the changes of Norovirus-specific serum and stool IgA, IgM and IgG, which will use the longitudinal data observed at all three time points.

For exploratory outcomes 23-26, a Fisher's Z-transformation will be applied to the Pearson correlations between change in total lymphocyte count and T cell subsets at Day 1 and 180 and clinical resolution of symptoms in both the treatment and placebo groups, which will then be compared using a Z-test.

Pharmacokinetics and Dose Response:

For exploratory outcome 27, plasma concentrations of nitazoxanide metabolites in subjects consenting for PK blood draws at two time points will be described and summarized. Descriptive statistics (e.g. n, mean, standard deviation, % CV, median, and range) will be calculated for each sampling time.

Cox proportional hazard regression models will be used to examine the dose response relationship of Day 7 and Day 21 nitazoxanide metabolite concentrations on time from randomization until initial clinical resolution of Norovirus symptoms for at least 48 hours through Day 180. Additional analyses of PK endpoints may be described in the SAP.

Natural History of Disease:

Exploratory outcomes 28-31 are all time-to-event outcomes. They will be analyzed similarly as exploratory outcome 1.

Exploratory outcome 32 will be assessed similarly to exploratory outcome 14.

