3.2. Endpoints

3.2.1. Primary Outcome Measure

- The time from randomization until initial clinical resolution of Norovirus symptoms for at least 48 hours through 180 days.

Clinical resolution will be assessed from the daily diary by the subject and will be defined as:

- Cessation of vomiting and,
- No stools classified by the Bristol Stool Chart as diarrhea (Type 6 or 7)

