5. SAMPLE SIZE CONSIDERATIONS

Sample size calculations assume a 50% reduction in the median duration of diarrhea for the nitazoxanide-treated group compared to those receiving placebo. The median diarrhea duration for the placebo group is assumed to be 135 days, while the median diarrhea duration for the treatment group is assumed to be 67.5 days. Given these assumptions, a sample size of 64 subjects in each arm (128 total) is required to achieve 90% power using the Log-Rank test. Accounting for a 20% attrition rate, final sample size will be 80 in each arm (160 total).

Though discouraged, the protocol allows for subjects in either study group to receive additional nitazoxanide after 28 days. Under the assumptions of treatment efficacy, additional treatment received by placebo subjects would reduce the median duration of symptoms for the placebo group to be closer to that of the nitazoxanide-treated group. It is assumed that subjects who would have the worst study outcomes (longest time to clinical resolution of diarrhea) will be the most likely to receive additional treatment. Subjects receiving additional treatment will be imputed as having the worst outcome (time to resolution censored at 180 days). Accounting for this imputation method, the power attained for the primary comparison was computed via simulation (R version 3.0.3). Estimated power is displayed in [Table 2](#), varying the proportion of subjects in each study group who receive additional treatment.

For example, if 15% of placebo subjects receive nitazoxanide, and 5-10% of subjects in the nitazoxanide-treated group receive additional treatment, the power is estimated to be 91.2%. Note that implausible scenarios (where substantially more nitazoxanide subjects receive additional treatment than do placebo subjects) have been omitted from the table.

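### Pearson correlations with the day of resolution or of first negative PCR cannot include subjects who never reach it, so the arms' correlations in SAP Tables 46 and 47 are not comparable

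*SAP*

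**What the plan says.** In SAP section 10, the relationship between change in total lymphocyte count and "the day of initial clinical resolution of symptoms will be evaluated using Pearson correlations". For the arm comparison, "A Fisher's Z-transformation will be applied to the Pearson correlations in both the nitazoxanide and placebo groups", followed by a Z-test with a p-value. Table 46 does this for the Day 1 to Day 180 change in lymphocytes and T-cell subsets. Table 47 does it for the change in serum and stool immunoglobulins to Day 28 and to Day 60. Each change is paired with the day of initial clinical resolution and, separately, with the first day of undetectable PCR.

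Protocol 11.4.5 sets out the same approach for exploratory outcomes 23 to 26: "a Fisher's Z-transformation will be applied to the Pearson correlations between change in total lymphocyte count and T cell subsets" and clinical resolution. It does not say that resolution is coded as a day.

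The resolution endpoint has a fixed horizon (SAP 3.2.1): "The time from randomization until initial clinical resolution of Norovirus symptoms for at least 48 hours through 180 days". SAP 8.1 and 8.2 analyse time to resolution and time to first negative viral load by Cox models and Kaplan-Meier curves. SAP 6.5 censors subjects who stop the diary before resolving.

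For the correlations there is no such rule. The immunogenicity population (SAP 6.3.4) does not require resolution. SAP 6.5 limits imputation to diary data for the primary endpoint. The shells of Tables 46 and 47 show correlations, intervals and p-values but no n.

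**The concern.** A Pearson correlation needs a number for every subject, and someone still symptomatic or still PCR-positive at Day 180 has none. Those are the persistent cases. The immunologic objective asks whether immune recovery goes with clearance, and Protocol 2.1 links defective T-cell function to prolonged shedding and T-cell recovery to clearance. Losing the persistent cases removes much of the contrast of interest.

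If the arms resolve at different rates, the range of days is also cut by a different amount in each. The two correlations can then differ even when the underlying association is the same. With no n in the shells, a reader of the report could not see that this had happened.

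**Working it through.** **Inputs.** Placebo: "The median diarrhea duration for the placebo group is assumed to be 135 days". Nitazoxanide: "while the median diarrhea duration for the treatment group is assumed to be 67.5 days" (both SAP 5). Follow-up is 180 days. Enrolment was 31 (SAP 14.2); a 16/15 split is assumed. The documents give neither the distribution of times nor the size of any association. The association was therefore set equal in both arms and varied. No PCR clearance rate is given, so only the clinical-resolution half of the tables is quantified.

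**1. The plan's own figure.** With exponential times, the proportion resolved by Day 180 is 1 − 2^(−180/median):
- placebo: 1 − 2^(−180/135) = 60.3%
- nitazoxanide: 1 − 2^(−180/67.5) = 84.3%
- mean: 72.3%

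The SAP says that "a sample size of 64 subjects in each arm (128 total) is required to achieve 90% power using the Log-Rank test", and the test is "conducted using a Log-Rank test at the 5% two-sided level of significance". For a hazard ratio of 2, Schoenfeld's formula needs 4(1.960 + 1.282)²/(ln 2)² ≈ 88 events, and 88/0.723/2 ≈ 61 per arm. Lachin-Foulkes gives 65 and Freedman 66. Simulated log-rank power at 64 per arm is 91.7%, against 91.3% in the SAP's Table 2. The exponential reading therefore matches the plan.

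**2. Share without a day of resolution.** From the medians alone it is 39.7% of placebo and 15.7% of nitazoxanide. Of 15 and 16 subjects, about 9 and 13.5 remain. If the hazard also varies with the immune change (log hazard ratio 0.5 per SD, medians held), the shares are 40.6% and 19.3%.

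**3. Effect on the correlation.** The same true association was set in both arms and only subjects with T ≤ 180 were kept. The ratio is the resolvers-only Pearson correlation divided by the full-data one.

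| Model | Nitazoxanide ratio | Placebo ratio |
|---|---|---|
| Proportional hazards, log HR 0.3 to 1.0 per SD | 0.54–0.86 | 0.30–0.68 |
| Gaussian copula, exponential times, rho −0.3 to −0.8 | 0.83–0.93 | 0.69–0.84 |
| Gaussian copula, log-normal times | 0.98–1.09 | 0.85–1.02 |

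- Proportional hazards, log HR 0.5: the full-data correlation of −0.40 becomes −0.24 (nitazoxanide) and −0.15 (placebo).
- Copula, exponential times, rho −0.5: −0.45 becomes −0.39 and −0.33.
- Extreme case, log HR 1.5: the ratio exceeds 1 (1.43 and 1.24), because the long tail depresses the full-data Pearson value itself.

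The loss is therefore usual but not universal.

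**4. The between-arm Z-test.** The statistic is [atanh(r₁) − atanh(r₂)] / √[1/(n₁−3) + 1/(n₂−3)], with n₁ and n₂ the resolvers. With equal true association it rejects in 3.7 to 5.3% of trials at 16/15. At 80/80 it rejects in 5.8 to 7.2% (copula) and 7.1 to 7.9% (proportional hazards, log HR 0.5 to 1.0).

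**5. Keeping the non-resolvers.** Under proportional hazards at log HR 0.5, Spearman's correlation with non-resolvers tied at the last rank is about −0.34 (placebo) and −0.37 (nitazoxanide), against −0.38 in full data. As a check on censoring alone, a Cox coefficient is the same in both arms: 0.50/0.50, 0.70/0.70 and 1.01/1.01 for true values 0.5, 0.7 and 1.0. At log HR 1 with 15 per arm, power against zero correlation within an arm is about 13% (placebo) and 26% (nitazoxanide) for resolvers-only Pearson, and about 62% and 69% for the ranked version. The SAP plans no such within-arm test, so these figures show only the information lost.

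**The case against.** The case on the other side is substantial, and parts of it stand.

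- **Resolvers-only is inferred.** The SAP is silent, and the protocol's wording would allow a yes/no coding that keeps everyone. That stands as a caution. But the SAP now names a day, and no value is provided for subjects without one.
- **A reader might infer that the plan halves the association.** The documents do not support a single figure. About half or more is lost under some proportional-hazards settings, and almost nothing under log-normal times in the nitazoxanide arm.
- **A reader might also infer that the Z-test would show a false treatment difference.** At 31 subjects it keeps its nominal size, and even at 80 per arm the excess is modest.
- **The planning medians are for duration of diarrhea.** The correlated variable is the first run of two consecutive symptom-free diary days (SAP 3.3), which may come earlier. The 40% is thus a planning figure. If nearly everyone resolves in both arms, the problem shrinks.
- **The outcomes are exploratory.** SAP 14.2 expects mainly descriptive analyses, and Tables 37 to 45 also address the immune response. This limits what is at stake. It does not rescue a descriptive correlation whose size depends on how many subjects resolved, and section 10 still prescribes p-values.

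**Conclusion.** The point holds in a limited form. Pearson correlation is the wrong tool for a time observed only through Day 180, and the plan has no rule for subjects without an event. If they drop out, about 40% of placebo and 16 to 20% of nitazoxanide subjects are lost under exponential times with the planning medians. The correlation is then usually weakened, with a retained share of about 0.3 to 1.0 depending on the model and on each arm's resolution rate. The displayed correlations are therefore not comparable between arms when resolution rates differ.

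The evidence does not support a claim of inflated false positives at the enrolled size (about 4 to 5%); at 80 per arm the rate would be about 6 to 8%. These sizes rest on an assumed equal association in both arms and on assumed time distributions. The PCR half of both tables has the same structure but cannot be sized from the documents.

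**What to change.** Replace Pearson in Tables 46 and 47 with a rank measure that keeps subjects without an event. The cleanest choice is Kendall's tau or a concordance measure that accepts right-censoring, with subjects censored at their last diary or last PCR result. Alternatively, use Spearman or Kendall tau-b with subjects documented as unresolved (or still positive) through Day 180 tied at the last rank.

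In either case, treat those who stopped diaries or terminated early as censored, not as unresolved. A Day 180 blood value does not prove follow-up to Day 180: the early termination visit repeats the Day 180 procedures (Protocol 7.4), and a subject can stop the diary and still attend.

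Print n, and the number without an event, per arm in both tables.

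A Cox model from a Day 28 or Day 60 landmark should be supplementary for Table 47, with a statement that it excludes earlier resolvers. Under the planning medians that is 1 − 2^(−28/67.5) = 25% of nitazoxanide and 1 − 2^(−28/135) = 13% of placebo at Day 28, and 46% and 27% at Day 60. The Day 180 change should not be a Cox predictor, because it is often measured after resolution.

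The cost is SAP wording and slightly more programming. The Fisher Z comparison must use a variance suited to the rank measure, for example by bootstrap or permutation. No new data are needed.
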